2.15.4 Challenges to identifying the legally acceptable representative for consent	
process	24
2.15.5 Failure of long read metagenomic sequencing	25
2.15.6 Reliable antibiotic consumption data	25
2.15.7 Global pandemic/Local epidemic	26
2.16 Future use of stored samples	26
2.17 Budget and finance	26
2.17.1 Budget justification	26

Version 5.0 21/05/2025

Executive Summary

Study type: This is a multi-site, extended observational case-control study with a preliminary cohort component.

Problem: Based on modelling, Sub-Saharan Africa is the region most affected by death due to antimicrobial resistance (AMR), but there is little AMR data from the region. Pneumonia remains a leading cause of death in children under 5 years old worldwide. To change this, we must understand how antibiotic selective pressure and healthcare exposure impacts AMR development and how AMR influences health outcomes in resource limited settings. The nasopharynx is a reservoir of organisms that cause pneumonia and their associated AMR. Metagenomic deep-sequencing enables identification of the nasopharyngeal resistome (NPR), all the genetic determinants of AMR within the nasopharyngeal bacterial niche. No study has examined whether human resistome composition is associated with health outcomes.

Objectives: Our study aims to answer the following research question; does hospital admission and antibiotic treatment for pneumonia generate a persistent hospital-acquired nasopharyngeal resistome in Malawian children, and is this associated with adverse health

 To measure how the diversity and relative abundance of the nasopharyngeal resistome of children hospitalised with pneumonia differs from the nasopharyngeal resistome of healthy children in the community.

outcomes in a resource limited setting? The primary objectives of this study are:

- To measure how the diversity and relative abundance of the nasopharyngeal resistome of children hospitalised with pneumonia differs from the nasopharyngeal resistome of children with pneumonia treated with antibiotics in the community.
- To investigate whether there is measurable persistence of a hospital-acquired nasopharyngeal resistome post-discharge, and whether this is associated with adverse health outcomes, including recurrent hospitalisation.

Methodology: This study will recruit 350 children aged 12-24 months in four groups: healthy children in the community, children with pneumonia in the community, children hospitalised with pneumonia and children re-hospitalised with pneumonia. The study will be conducted at Ndirande community healthcare centre, Gateway primary care centre and Queen Elizabeth Central Hospital. Nasopharyngeal swabs (NPS) and urine samples will be taken at recruitment and follow up study visits; NPS will undergo metagenomic sequencing to identify the nasopharyngeal microbiome (NPM) and NPR, urine samples will be used for an

NP Resistome Study

Version 5.0 21/05/2025

Page 6 of 30

[figure not shown]

antibiotic assay. Demographics, co-morbidities, health outcomes and antibiotic exposure will be recorded at recruitment for all participants, and subsequent study visits where applicable. **Expected results and dissemination:** The study is expected to describe NPR evolution following antibiotic selective pressure and healthcare exposure for pneumonia in Malawian children. It will provide contemporary data on AMR carriage in the community, hospital admission and re-admission rates with pneumonia, and antibiotic use patterns. A report of the study will be submitted to the College of Medicine Research Ethics Committee (COMREC), Blantyre district health office and Liverpool School of Tropical Medicine (LSTM). The findings will be presented at international scientific conferences and published in peer reviewed medical journals.

Version 5.0 21/05/2025

Page 7 of 30

1.0 Background

Antimicrobial resistance (AMR) is a threat to global public health, predicted to cause 10 million deaths annually by 2050 [1]. Based on modelling, Sub-Saharan Africa is the region most affected by AMR-attributable death, but there is little AMR data from the region [2]. To change this, we must understand how antibiotic selective pressure and healthcare exposure impacts AMR development and how AMR influences health outcomes. We need comprehensive microbiological and epidemiological data from resource limited settings, where data are sparse [2,3], to design appropriate public health interventions [4].

Pneumonia is a leading cause of death in children under 5 years old worldwide [5] and one of three syndromes that dominate the global burden of AMR [2]; it remains a diagnostic challenge [6]. The nasopharynx is a reservoir for pneumonia pathogens, including *Streptococcus pneumoniae* and *Staphylococcus aureus*, which are common causes of AMR-attributable death [2].

Metagenomic deep-sequencing enables identification of all the antibiotic resistance genes (ARGs; genetic code that produces antibiotic resistance in a bacteria) and mobile genetic elements (MGEs; genetic code that carries ARGs between different bacterial species), that form the resistome in a microbial niche. There is limited data on NPR evolution [5]; studies are characterised by small samples sizes and single sampling time points. Comparison between studies is limited by differing populations, deoxyribonucleic acid (DNA) extraction methods and sequencing techniques [5].

Many of these studies do not examine the NPM; they use targeted sequencing techniques to focus on specific resistance determinants [7–9], or culture enrichment to focus on Streptococcal species, particularly *S. pneumoniae* [7,9–12]. This biased analysis creates the misleading impression that the NPM and NPR are dominated by *S. pneumoniae* [13]; other pathogens in the nasopharynx do exhibit AMR, including *H. influenzae* and *S. aureus* [14]. Importantly, a more diverse microbiome may facilitate exchange of ARG within a resistome [13]. *S. pneumoniae* readily acquires ARG by horizontal gene transfer (HGT; movement of genetic code from one organism to another) on MGE [15], particularly in the context of multiple serotype carriage [11], and from environmental DNA by transformation [15].

Existing NPR studies do highlight some interesting themes: whilst many ARG are associated with streptococcal species, β lactamase genes are predominantly found on non-

NP Resistome Study

Version 5.0 21/05/2025

Page 8 of 30

streptococcal species, which may provide a source for HGT between species [12]. The neonatal nasopharynx is colonised by ARG from environmental sources [8,16]; this is particularly relevant in hospitalised neonates, who may acquire nosocomial bacteria with ARG on MGE that have potential for HGT to pneumonia pathogens within the NPM.

1.1 Rationale

There is limited data on NPR evolution under antibiotic selective pressure and following exposure to a hospital environment. No study has examined whether human resistome composition (ARG abundance and diversity) is associated with health outcomes.

Malawi has limited healthcare resources and a high incidence of pneumonia in children aged 12-24 months [17]. Our study will describe the impact of antibiotic selective pressure and exposure to the hospital environment on the NPR of Malawian children with pneumonia. The study will investigate the hypothesis that among these children a hospital-acquired NPR is associated with adverse health outcomes following discharge, by examining whether NPR composition is associated with hospital readmission.

We have chosen to focus on hospital re-admission as an adverse outcome related to AMR in pneumonia, because severe pneumonia requiring hospitalisation is more commonly bacterial in aetiology [6]; thus, re-hospitalisation is more likely to reflect the impact of AMR in bacterial pneumonia. Alongside the World Health Organisation (WHO) markers of severity in pneumonia, a range of adverse health outcomes of AMR in bacterial pneumonia will be recorded, including additional episodes of pneumonia, additional courses of antibiotics and their duration, and mortality outcomes.

Antibiotic use prior to seeking healthcare input is common in Malawi; 70% of patients report self-administration of antibiotics in this setting [18], which correlates with recent unpublished evidence of antibiotic activity detected in urine assays in hospitalised children.

Disentangling the impact of antibiotics and hospital admission on the resistome could inform public health interventions, including prescribing practices and hospital admission policies.

1.2 Hypothesis

Our hypothesis is that antibiotic use will select for a less diverse group of ARGs, dominated by ARGs that produce phenotypic resistance to the class of antibiotics to which an individual has been exposed; that ARGs will be more abundant in the NPR at discharge from

NP Resistome Study

Version 5.0 21/05/2025

Page 9 of 30

hospital, due to microbiome dominance by the pneumonia pathogen; and that exposure to the hospital environment will drive acquisition of ARGs on MGEs, which could lead to more HGT. Children who are re-admitted to hospital with pneumonia within 3 months of a previous hospitalisation will have a more 'high-risk' NPR than those who remain in the community after hospital discharge, with a greater abundance of ARGs, less diverse NPR and greater prevalence of MGEs.

1.3 Study Objectives

1.3.1 Broad Objective

To determine whether hospital admission and antibiotic treatment for pneumonia generate a persistent hospital-acquired nasopharyngeal resistome in Malawian children, and whether this is associated with adverse health outcomes in a resource limited setting?

1.3.2 Primary Objectives

- To measure how the diversity and relative abundance of the nasopharyngeal resistome of children hospitalised with pneumonia differs from the nasopharyngeal resistome of healthy children in the community.
- To measure how the diversity and relative abundance of the nasopharyngeal resistome of children hospitalised with pneumonia differs from the nasopharyngeal resistome of children with pneumonia treated with antibiotics in the community.
- Investigate whether there is measurable persistence of a hospital-acquired nasopharyngeal
 resistome post-discharge, and whether this is associated with adverse health outcomes,
 including recurrent hospitalisation.

1.3.3 Specific Secondary Objectives

- 1. To measure the rate of hospital re-admission with pneumonia in children aged 12-24 months over a 4-week period in a single tertiary referral hospital in Malawi.
- 2. To measure antibiotic use in the community in children aged 12-24 months in Malawi.

2.0 Methodology

2.1 Study design

This is a multi-site, extended case-control study with a preliminary cohort component to assess the evolution of the NPR under selective pressure of antibiotic use and hospital admission for pneumonia in children aged 12-24 months in Malawi. The study will be led by the PhD student, [name], as a PhD fellowship.

NP Resistome Study

Version 5.0 21/05/2025

Page 10 of 30

In the preliminary cohort component, healthy children in the community will have a NPS collected at the first study visit, to determine the baseline community resistome through metagenomic sequencing (see Figure 1).

To assess the impact of oral antibiotics on the NPR, children presenting with pneumonia to community healthcare clinics, Ndirande and Gateway Primary Care Centre (GPCC), will have a NPS collected at the first study visit and 3-months post-recruitment, to determine the antibiotic-exposed resistome through metagenomic sequencing (see Figure 1).

To understand the impact of broad-spectrum intravenous antibiotics and exposure to a hospital environment on the NPR, children hospitalised with pneumonia (without any hospital admission 6 months prior) to Queen Elizabeth Central Hospital (QECH) will have a NPS collected at the first study visit, discharge and 3-months post-recruitment to determine a hospital-acquired resistome through metagenomic sequencing (see Figure 1).

[figure not shown]

Figure 1. Preliminary cohort component of the study. The yellow diamonds represent the key samples groups for NPR comparison.

The case-control component of the study will examine whether a hospital acquired NPR is associated with adverse health outcomes, specifically re-admission to hospital with pneumonia. Children hospitalised to QECH with pneumonia (without admission 6 months prior), who are not re-admitted within 3 months will form the control group (see Figure 2); these participants will have a NPS will be collected at the first study visit (within 24 hours of admission to hospital), discharge from hospital and 3-months post-recruitment to assess for a hospital-acquired resistome. Those hospitalised within the preceding 6 months will be

NP Resistome Study

Version 5.0 21/05/2025

Page 11 of 30

excluded from this control group, to prevent confounding. Children admitted to QECH with pneumonia within 3 months of a previous hospital admission with pneumonia will form the case group; these participants will have a NPS collected at the first study visit (within 24 hours of admission) only, to assess for a hospital-acquired resistome. Health passport screening and carer-reporting will be used to establish prior hospitalisation.

A 4-week audit of hospital re-admission rates of children aged 12-24 months with pneumonia will be conducted at QECH before starting study recruitment, to further inform sample size calculations.

[figure not shown]

Figure 2. Case-control study design to examine whether a hospital-acquired NPR is associated with re-admission to hospital with pneumonia.

Two flocked NPS will be taken at the first study visit from all study participants; one NPS will be stored for viral PCR analysis (outside this fellowship), the other NPS will undergo metagenomic sequencing. Viral PCR analysis of the NPS will seek to identify RNA pathogens most associated with severe acute respiratory infections requiring hospitalisation in this population: Respiratory Syncytial Virus (RSV) and Influenza A [19]. Only one NPS for metagenomic sequencing will be taken from study participants at subsequent study visits e.g. discharge from hospital and 3-month follow-up. All NPS will be stored at -80°Celsius, following an established protocol [20], prior to DNA extraction using mechanical and chemical lysis to optimise the yield of DNA from low-biomass samples dominated by grampositive organisms. Extracted DNA will undergo metagenomic sequencing. Metagenomic data analysis will be performed using an open-source bioinformatic pipeline that I will develop to determine NPM and NPR composition. A urine sample will also be collected from

NP Resistome Study Version 5.0 21/05/2025

Approved by
College of Medicine

16/06/2025

(COMREC)
Research and Ethics Committee

Page 12 of 30

each participant at the first study visit, and stored for antibiotic assays (outside this fellowship), to assess the impact of antibiotic use prior to seeking healthcare input on NPR composition.

Age, gender, co-morbidities, mid-upper arm circumference, pneumococcal vaccination status, antibiotics received 7 days prior to recruitment, haemoglobin level and malaria screening results will be recorded for all participants at recruitment; exposure to tobacco smoke from a household contact and whether the participant was breastfed in their first 3 months of life will also be recorded, as these are independently associated with pneumonia requiring hospitalisation in high-income settings [21]. Mode of childbirth (vaginal versus caesarean section) will also be recorded, as this influences early NPM development, and may be associated with childhood respiratory health [22]. To assess for acquisition of MGEs from the hospital environment, we will record data on duration of hospitalization and incidence of shared bed-spaces for hospitalised study participants, including number of occupants and number of days in a shared bed-space. Shared hospital bed-spaces will be sampled using a swab for metagenomic sequencing. Groups undergoing repeat NPS at 3 months will have health outcomes (including mortality), healthcare interactions (including healthcare facility and hospital attendance/admission) and antibiotic exposure recorded.

Groups being admitted to hospital will have WHO markers of severity in pneumonia recorded, including presence of the following at the time of admission: central cyanosis, oxygen saturations less than 90%, inability to feed, vomiting, convulsions, lethargy and impaired consciousness. To assess for potential influence of healthcare seeking behaviour on hospital re-admission, groups presenting to healthcare clinics and/or hospitals with pneumonia will have the educational level of the parents recorded, and the distance travelled to the healthcare clinic.

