2.5 Sample size and calculations

There is no established method for sample size calculation in resistome studies; we use an approach for microbiome studies [25]. Differences in gut plasmidome composition have been detected with 41 participants per group [26], but NPR has a lower biomass than gut resistome, therefore the resistome is likely to be less diverse, with a lower relative abundance of ARGs. NPR analysis 3.5 years post-antibiotic exposure in a cluster-randomised trial of mass-azithromycin administration shows a trend toward decreased NPR diversity (p = 0.07) in azithromycin clusters when compared to placebo clusters, with just 25 samples per group (unpublished data).

We have used the measured difference in relative abundance of a specific macrolide ARG (ermX) 3.5 years after mass-azithromycin administration (unpublished data) as a medium effect size that maybe clinically relevant (Δ = 0.505). Using the approach for microbiome studies, accepting 90% power and 5% type I error (95% confidence interval),

NP Resistome Study

Version 5.0 21/05/2025

Page 15 of 30

we've calculated that we will require a sample size of 83 participants in each group to detect this effect size, using the formula $n=2(Z_{1-\alpha/2}+Z_{1-\beta})^2/\Delta^2$ [25].

In total we aim to recruit 350 study participants: 83 healthy community participants, 92 participants with pneumonia in the community, 92 participants admitted to hospital with pneumonia and 83 participants re-admitted to hospital with pneumonia. Study groups with a sample size of 92 participants permit a 10% loss to follow up.

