2.7.3.6 Exclusion criteria for children hospitalised with pneumonia

- Severe anaemia, with a recorded haemoglobin level < 70 grams per Litre.
- Currently taking long-term antibiotic prophylaxis, TB treatment or immunosuppressive medications.
- Diagnosis of an immunosuppressive illness, including HIV infection.
- Hospital admission within the past six months.

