2.7.3.7 Inclusion criteria for children re-hospitalised with pneumonia

- Child aged between 12-24 months.
- Presence of all of the following symptoms: fever, cough, difficulty in breathing and fast breathing.
- Participant has been prescribed antibiotics for treatment of a lower respiratory tract infection on this presentation.
- Hospital admission to ANY hospital with a lower respiratory tract infection within the past 3 months.

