2.7.3.8 Exclusion criteria for children re-hospitalised with pneumonia

- Severe anaemia, with a recorded haemoglobin level < 70 grams per Litre.
- Currently taking long-term antibiotic prophylaxis, TB treatment or immunosuppressive medications.
- Diagnosis of an immunosuppressive illness, including HIV infection.

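### The 6-month look-back meant to prevent confounding applies to controls but not to the period before the cases' index stay; the 92 hospitalised children also leave no room for re-admissions, and the control rule is silent on death

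*Protocol*

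**What the plan says.** **Controls.** Section 2.1 takes children admitted to QECH with pneumonia "who are not re-admitted within 3 months will form the control group". Children with an admission in the 6 months before that stay are "excluded from this control group, to prevent confounding", and section 2.7.3.6 lists the matching exclusion: "Hospital admission within the past six months". The same children are to be swabbed at admission, "discharge from hospital and 3-months post-recruitment to assess for a hospital-acquired resistome".

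**Cases.** Section 2.7.3.7 requires "Hospital admission to ANY hospital with a lower respiratory tract infection within the past 3 months". Section 2.7.3.8 has three exclusions (severe anaemia, long-term medication, immunosuppression), the last being "Diagnosis of an immunosuppressive illness, including HIV infection". None concerns admissions before the index stay.

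**Numbers.** Section 2.5 derives 83 per group and enrols 92 hospitalised children and 83 re-admitted children. On the margin it says: "Study groups with a sample size of 92 participants permit a 10% loss to follow up".

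**Death.** Section 1.1 lists mortality among the adverse outcomes, and section 2.1 records it in groups with a 3-month swab. The control rule does not refer to it.

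**The concern.** The case-control component asks whether a hospital-acquired resistome is associated with re-admission, so earlier hospital stays are part of the exposure under study. The protocol treats a recent earlier admission as a confounder and removes it from one side only. A case may have two or three admissions in the months before the index stay; a control can have none in the 6 months before. If hospital contact adds resistance genes, as the hypothesis in section 1.2 supposes, cases would look more resistant partly because eligibility allowed them more hospital contact.

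Two further points come from the same definition. Re-admission within 3 months removes a child from the control group, yet the sample size makes no allowance for it. And a child who dies without re-admission meets the rule's wording literally, although the protocol counts death as an adverse outcome.

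**Working it through.** **1. The look-back on each side**

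| | Admissions before the index stay | Index stay | Source |
|---|---|---|---|
| Controls | None in the preceding 6 months | Current stay at QECH | 2.1, 2.7.3.6 |
| Cases | No limit | An admission at any hospital in the past 3 months | 2.7.3.7, 2.7.3.8 |

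Cases cannot meet a 6-month rule at their current admission, because a recent stay is what makes them cases. The rule could, however, be applied to the 6 months before their index stay, and the protocol does not do so.

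The analysis does not clearly repair this. Section 2.9.1 uses unadjusted t-tests. The confounders named in section 2.9.2 are co-morbidities, nutritional status, duration of admission and severity; earlier admissions are not named. The data list in section 2.1 names neither the number of a case's earlier admissions nor the index hospital.

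The bias would be the share of cases with an earlier admission multiplied by the resistome shift per earlier admission. The documents give neither input, so only the direction can be stated.

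**2. Control numbers**

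Inputs from section 2.5: effect size 0.505, two-sided alpha 5%, power 90%, 92 enrolled, 10% loss.

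- Plan's own figure: n = 2(1.960 + 1.282)² / 0.505² = 82.4, rounded up to 83. This reproduces.
- Allowance: 83 / 0.9 = 92.2, and 92 x 0.9 = 82.8. The loss allowance uses the whole margin (9 of 92, or 9.8%).
- Re-admission over 3 months is an assumption. Section 2.15.1 uses 18% over 6 months, a severe-anaemia figure, as a stand-in. At constant hazard this is 1 − √0.82 = 9.4% over 3 months; halving it gives 9%.
- Controls left = 92 x 0.9 x (1 − r). Power is by normal approximation against 83 cases at 0.505: Φ(0.505 / √(1/n + 1/83) − 1.96).

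| Assumed r | Controls left | Power | Enrolment needed to keep 83 controls |
|---|---|---|---|
| 0% | 82.8 | 90.2% | 92.2 |
| 2% | 81.1 | 89.9% | 95 |
| 5% | 78.7 | 89.4% | 98 |
| 9.4% | 75.0 | 88.7% | 102 |
| 18% | 67.9 | 87.0% | 113 |

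The last column is 83 / (0.9 x (1 − r)), rounded up after the first row. The 18% row takes the full 6-month figure as an upper bound.

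Detectable effect at 90% power with 75 v 83: (1.960 + 1.282) x √(1/75 + 1/83) = 0.516.

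With no loss at all, 92 x (1 − 0.0945) = 83.3, so the target would still be met.

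**3. Death**

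Read literally, a child who dies after discharge without re-admission is a control. Read with the swab schedule, the child cannot give the 3-month sample and would probably be treated as lost. The protocol does not choose between the two. If deaths are removed on top of 10% loss and 9.4% re-admission, an assumed 3% to 5% mortality leaves about 73 to 71 controls, with power about 88%. If deaths already sit within the 10%, nothing changes.

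**The case against.** **On the look-back.** No size can be shown. A reader might put a figure on the bias by assuming a share of cases with earlier admissions and a shift of about 0.5 SD. Since 0.5 is nearly the planning effect of 0.505, that only returns the assumed share as a percentage of the effect; the documents do not support it. The confounder list in section 2.9.2 is open-ended, so earlier admissions could be added. But no control has one by design, so adjustment has nothing to compare. Admitting an index stay at any hospital is consistent between sections 2.1 and 2.7.3.7 and is not an error.

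**On numbers.** A reader might infer that controls must fall below 83. That needs both the full 10% loss and re-admissions on top. The 18% comes from a condition this study excludes, section 2.15.1 says no pneumonia re-admission data exist for the region, and a 4-week audit is planned to inform the sample size. All of this stands. A reader might also combine this with a shortage of cases: 500 a year x 9% = 45, giving about 76% power with 75 controls. With 83 controls it would be about 78%, so the control shortfall costs about 1.5 points there too. The rest is the case shortage, for which section 2.15.1 lists contingencies.

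**On death.** A reader might infer that the plan counts deaths as controls. It does not say so, and the 3-month swab points the other way. Nor do the documents support merging death with re-admission into one case definition: cases are swabbed within 24 hours of re-admission, a sample a child who died without re-admission cannot give.

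What remains is the one-sided look-back, the missing allowance for re-admission and the silence on death.

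**Conclusion.** The point holds in three parts of unequal weight. The main one is the one-sided look-back. The protocol names a source of confounding and controls it for controls only, so cases may bring extra hospital exposure that favours the hypothesis. The direction follows from section 1.2; the size cannot be estimated from the documents.

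The control count is a minor planning error. At the stated 10% loss, any re-admission takes controls below 83. Assumed re-admission of 2% to 9.4% leaves about 81 to 75, and at 75 the cost is about 1.5 points of power (90.2% to 88.7%) and a detectable effect of about 0.52 instead of 0.505.

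The treatment of deaths is a gap in the definition, not a demonstrated misclassification. It matters because the third primary objective concerns adverse outcomes. None of this invalidates the study; all of it can be settled in the protocol text.

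**What to change.** 1. For cases, record from the health passport the number and dates of admissions in the 6 months before the index stay, and the index hospital. Pre-specify a case-control analysis restricted to cases with no such admission, alongside the all-cases analysis. The cost is a few CRF fields from a document already screened, and fewer cases in the restricted analysis. With cases scarce, the restricted set should stand beside the full set and not replace it.
2. In section 2.5, restate the expected number of controls and the power with re-admission allowed for: about 75 controls, 88.7% power and a detectable effect of about 0.52 at the 9.4% assumption, updated from the audit. If 83 controls are to be kept, enrolment would rise to 95 to 102 for re-admission of 2% to 9.4%. Restating the figure costs nothing; enrolling more costs recruitment time and budget.
3. Define controls as alive and confirmed not re-admitted at the 3-month contact, and report deaths separately as an adverse outcome. This is a wording change, since mortality is already recorded; any deaths not already within the 10% loss would lower the control count slightly further.
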